- **Near transfer** to non-trained cognitive domains^{99, 100} and **far transfer** of gains (improved motor skills^{65, 101}) have been reported after C-REM interventions. The ACTIVE study reported that participants had less difficulty with instrumental ADLs 5 years after training (without boosters).^{23, 101}
- A **broad approach** targeting multiple domains may be more effective than targeting a single or limited set of cognitive processes. This may be especially relevant to gait which engages multiple cognitive processes.²⁰

B.5.c. COGNITIVE REMEDIATION PILOT (J Gerontol Med Sci 2010²⁶ 2011¹⁶) We conducted a pilot study to test efficacy and feasibility of C-REM. We recruited 24 frail seniors (exercise \leq once weekly and gait speed < 1 m/sec) from the community using our well-established recruitment procedures (described in C.5.12). They were randomized to C-REM and 12 to 'usual care.' The C-REM group got 24 (50 min) sessions over 8 weeks (3/week). Controls attended a fitness workshop and had telephone follow-up. Study assessments were done at baseline and post-intervention. **Transportation** was provided to all participants to ensure adherence to protocol as well as to avoid any indirect increased physical activity as a result of traveling to our center. Due to space limits a summary of main findings is provided. Full details are available in our published papers.^{16, 26}

Mobility: At baseline, there were no significant group differences in age, gender, MMSE score or frailty status. 10 C-REM and 10 controls completed the study. Post-intervention, no subject started an exercise program or reported increase in physical activity, though 2 C-REM participants started using computers.

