C.6. Screening visit. Potential recruits who meet eligibility criteria on the telephone are invited for in-person screening and are told that they will receive a *phone call reminder* the evening before the appointment. All participants recruited through population lists and Clinical Looking Glass will receive the same screening procedures. Written consent and screening will occur in our research center (see Facilities). On arrival, potential participants will review study information and sign consent. Study clinicians will determine final eligibility. Eligible subjects are randomized for interventions at the initial visit.

C.7. Subject eligibility criteria. While healthy or disabled seniors may also benefit from C-REM, we chose to focus first on efficacy (rather than effectiveness) of secondary prevention using C-REM in sedentary frail seniors, a high risk for disability yet highly prevalent group in USA.^{29, 135}

Inclusion criteria. 1) age 70 and older; 2) sedentary (exercises \leq 1/week^{43, 129-131}); 3) Ambulates with or without an assistive device. Individuals who require assistive devices will be enrolled if they meet the other criteria; 4) SPPB score \leq 9¹³⁶ corresponding to frail range; 5) gait velocity \leq 1.0cm/s (same criterion was used in our pilot study).^{137, 138} Greater mobility benefits of C-REM in slow walkers and frail older adults is suggested from findings in our and other pilot studies.²⁶⁻²⁸

Exclusion criteria: 1) Serious chronic or acute illness. *Mere presence of diseases will not be used to exclude if well controlled.* 2) Musculoskeletal limitations that prevent completion of mobility tests. 3) Hospitalized in past 6 months or plans for surgery affecting mobility in next 6 months. 4) Dementia (screened as above); 5) Participation in any C-REM or other cognitive training in the past 12 months.

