C.8. Randomization. The Efron ('biased coin') procedure¹³⁹ will be used to assure near-equal sample sizes and good representation on three variables of interest (gender, age $<$ or $>$ 80 years, and NPW speed $<$ or $>$ 70 cm/s¹³⁷) in both groups. Also see C.15.e. It will not be efficient to randomize by more categories. Besides, variables such as illness are highly correlated with speed and age, and are dealt analytically as covariates. Group assignment will be dispensed in sealed opaque envelopes generated by [name] using sequential study numbers so that the assistant who enrolls the participants will be blinded to randomization assignment of the next participant until assigned. [name] will not be involved with subject testing or interventions.

C.9. Sample size. We will enroll **420 seniors (210 per group)**. Power and assumptions in section C.14.1.

[figure not shown]

Figure 3. Subject Flow

C.10. Blinding. Given the nature of our interventions, double-blinding both subjects and testers will not be feasible. But we will include a number of methods (besides randomization) to reduce bias.

- Selection bias will be reduced by concealing treatment allocation until the subject is entered into trial.¹⁴⁰
- Primary outcome is an objective endpoint (gait speed/SPPB) and not subjective mobility complaints.¹⁴⁰
- C-REM and health control interventions will be done in different sites and at non-overlapping times.
- The assessment team (and location) will be separate from intervention team.
- Participants and study staff will be instructed not to disclose group assignment or details of interventions.
- **Post-intervention questionnaire** (C.12.5) to assess maintenance of blinding.

C.11. Interventions. Both interventions will be given 3 times weekly for 8 weeks without crossover. C-REM program is supervised by [name] and the health education control by [name]. A **manual of operations** for all study activities will be developed during study setup (see **Table 3** in E.2.). Our intervention is based on a social cognitive model that views health behavior as being acquired and maintained through a complex set of behavioral, cognitive, and environmental conditions. Social cognitive theory concepts will be combined with strategies derived from applications of the Transtheoretical Model to mobility interventions^{59, 141} (e.g., consciousness raising early in the program; reinforcement management later in the program).^{59, 142}

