Outcomes will be assessed by a research assistant supervised by [name] whom will not participate in other aspects of this RCT. Baseline study assessments done in the first week is limited to **90 minutes over 1 day** to avoid fatigue. Testing time per subject is less than in our ongoing aging studies (~180 min), and was demonstrated to be feasible in our pilot study.²⁶ Telephone assessments are **10 minutes**. Post-intervention assessments conducted at 9 weeks, 6 months, and 12 months will be limited to 90 minutes.

Our group developed or validated many of the primary and secondary outcome measures in this RCT (see resumes and refs^{11, 16, 20, 48, 49, 51, 64, 129, 130, 145-154}). We have over 12 years continuous NIH funding for training and supervising assistants to administer these measures in various elderly populations.

C.12.1. PRIMARY OUTCOME (Mobility): We selected the following three primary outcomes to test the efficacy of the C-REM intervention.

C.12.1.a. Gait speed: Gait speed was recommended to FDA as the preferred outcome for RCTs³⁰ because of its good validity, reliability, sensitivity to change, and predictive validity for multiple adverse outcomes.³⁰ We have reported that gait speed highly correlates with mobility related activities in our community.¹⁵⁵

Method: Research assistants will conduct gait evaluations using a 28-foot computerized mat (20-feet recording surface) with embedded pressure sensors (GAITRite). The mat has 4 feet at each end without sensors to account for initial acceleration and terminal deceleration. Subjects will be asked to walk on the mat at their 'normal walking speed' in a quiet and well-lit room. Monitoring devices will not be attached. Our primary outcome is speed (cm/s). However, multiple gait parameters (see ref¹⁴⁷) will be obtained and available for analyses¹⁴⁷ (P1, P.2.1). Subjects will also be assessed walking the course at their fastest speed.

Reliability: We have reported excellent test-retest reliability of gait speed on GAITRite (Kappa >0.9).^{46, 128} Gait speed correlates highly with complaints of mobility limitations, falls and dementia in our studies.^{128, 134}

Practice effects: Gait speed improved only by <2% when tested twice 8 weeks apart in controls in our pilot study suggesting that longer intervals between gait assessments may help minimize practice effects.

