- We will use **intention to treat (ITT) analysis**, which includes all randomized participants in the groups assigned, regardless of adherence with entry criteria, whether C-REM was received, and subsequent withdrawal or deviation from the protocol.¹⁹⁴ ITT analysis is pragmatic because it admits noncompliance and protocol deviations, and gives an unbiased estimate of the intervention effect. Handling missing data is a major issue in ITT, and is dealt with by imputation or sensitivity analysis.¹⁹⁵⁻¹⁹⁷ The linear mixed effects

model is good in handling missing data due to drop out assuming MAR mechanism.^{193, 198-200} Our statistician, [name], is very experienced in these methods; see C.15.²⁰¹⁻²⁰³

Last observation carried forward is used to deal with missing data, but there are major limitations (see refs^{204, 205} for reviews). Hence, we do not propose to use this method.

- We will utilize closed testing methods, involving step-wise procedures, for addressing multiple comparisons/multiple testing, since they are more powerful than single step methods (e.g. Bonferroni).²⁰⁶
- If sessions attended vary, 'dose' effect will be examined in both groups – discussed in C.11.
- **Mediation analysis** (product of coefficients method²⁰⁷) will be conducted to examine whether depression, psychosocial measures (mood, self-esteem, and self-efficacy) as well as changes in proximal cognitive outcomes (attention and EF) mediates C-REM effects on gait speed in NPW and WWT conditions.
- **Gender:** Almost all observational and intervention studies in aging populations have a female preponderance; reflected in our target recruitment table. This gender distribution has been our experience recruiting over 2000 participants to various aging studies at our center for over 10 years.

While gender differences in EF are reported,^{190, 191} there is insufficient information to assume that there will be gender-based differences in C-REM effects on mobility. Gender explained only a very small portion (2.2%) of the individual variance in EF dependent Card Sorting test in a large NIH toolbox validation study.¹⁹⁰ Repeated training on an EF task (DSST) improved performance on the test; but did not show gender differences.¹⁹² The ACTIVE study reported that adjusting for gender did not change main results in their intervention study.⁶⁵ Hence, we decided against gender-based recruitment.

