- e. **Speed ≤70 cm/s.** We will use this widely used slow gait cutscore as one of our randomization variables.¹⁵⁰ If we exclude all with slow gait we may bias against enrolling oldest subjects who have mean gait speeds that are lower than the 70 cm/s cutscore.³⁰ We will stratify analysis by this cutscore and examine effects.
- f. **Feasibility.** In our pilot study,¹³ 50% of subjects met Fried frailty criteria⁴³ but completed interventions. We propose to over-enroll by 20% to account for any attrition. We have incorporated multiple methods to promote adherence and reduce possibility of missing data. We have also built in stopping rules.
- g. **Which aspects of the cognitive training are responsible for improvements?** While it is important to show that the overall C-REM program improves mobility; Mindfit also tracks training patterns that will help us refine the C-REM program for future studies. The availability of such extensive data will enable us to

develop individual and/or group models of growth using techniques such as growth curve analysis. One can also investigate the relation between growth patterns on tasks and mobility benefits. Dose is also studied.

h. Negative findings: We will employ several strategies to assess potential negative findings. 1) We showed that the protective effect of attention/EF against decline in gait speed is moderated by cognitive reserve.⁶ We will evaluate whether cognitive reserve moderates the effect of C-REM on mobility; 2) We will apply for additional funding to establish a bio-repository for this cohort. This will provide an opportunity to evaluate whether genetic factors or biomarkers such as brain derived neurotrophic factor (BDNF) may mediate the effect of C-REM on mobility.²⁰⁸⁻²¹⁰ 3) We have the opportunity to examine C-REM effects on other mobility, cognitive, mood, and psychosocial outcomes.

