
E. HUMAN SUBJECTS

E.1. Study population:

The characteristics of the subjects, recruitment methods, inclusion and exclusion criteria, and minimum numbers to be studied are described in Section C. The study interviewer will conduct the initial telephone-screening interview. Potential subjects will be invited for further in-person evaluations. Study evaluations, enrollment, and in-person interventions will be done at our research center. The study clinician ([name]/[name]) will diagnose and exclude cases following clinical and neuropsychological testing. The statistician will assign unique study ID to each subject. Research assistants at enrollment will determine eligibility.

General inclusion criteria:

1. Adults aged 70 and older, residing in the community. The age criterion is intended to maximize rates of incident mobility disability.
2. Plan to be in area for next three or more years.

3. Able to speak English at a level sufficient to undergo our cognitive assessment battery.
4. Ambulatory. Subjects are classified as 'non-ambulatory' if they are unable to leave the confines of their home and attend a clinic visit. These include subjects who are bed-bound as a result of severe medical illness or those who require assistive medical devices (respiratory support or ventilators) that cannot be transported or those who cannot complete our gait protocols. **We will not exclude subjects who use walking aids (canes, crutches) for ambulation. Subjects who require walking aids to walk outside but are able to complete our gait protocols without an assistive device or the assistance of another person will not be excluded.** Subjects who become non-ambulatory during follow-up will continue participation in the study via telephone interviews and mailed questionnaires.
5. Gait velocity ≤ 1.0 cm/s.
6. Short Physical Performance Battery score ≤ 9 .

General exclusion criteria (one or more criteria):

1. **Presence of dementia** (Telephone based Memory Impairment Screen score (T-MIS) of <5 , AD8, or dementia diagnosed by study clinician at initial visit). These cut scores and procedures have been validated in our and other aging studies.

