The open session report will focus on patient accrual and demographics, data completeness, and other study performance measures. Only aggregate data will be presented during the open session (i.e., not segregated by treatment). The closed session report will divide study participants according to coded treatment assignment (C-REM or health education control), comparing participant demographics and baseline characteristics, rates and reasons for treatment discontinuation and loss to follow-up, and rates of serious adverse events. The interim efficacy analysis will be included only in the report for the closed session. In addition to reports prepared by the statistician, the Principal Investigators may prepare a report addressing concerns he anticipates the DSMB will have regarding the conduct of the study.

The interim data reports will include:

- Monthly and cumulative accrual
- Baseline characteristics, overall and by treatment group
- Summary of completeness and quality of data collection forms
- Status of enrolled patients, overall and by treatment group
- Assessments of whether study personnel have followed eligibility criteria and other protocol requirements
- Assessment of participant adherence, overall and by treatment group
- Sample size assumptions
- Outcome rates, overall and by treatment group along with monitoring boundaries for efficacy and futility (if the planned interim look is due)
- Listing of serious adverse events by participant ID number and a table of event-specific cumulative rates, overall and by treatment group
- A summary description of all serious adverse events

Only the closed session report will include the comparisons by treatment group.

E.8.f. Adverse Event Monitoring:

Process: DSMB chair, to be named, will perform data and safety monitoring on an ongoing basis. She/he will not be otherwise involved in assessments or interventions in this clinical trial. The PIs or research staff will see all volunteers. All abnormal findings from the clinical, mobility, and neuropsychological assessments done on Day 1 will be documented on a case report form and reviewed by the DSMB chair. Periodic audits from the AECOM-CCI ensure compliance with confidentiality guidelines and adverse events monitoring.

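### Both eligibility lists give the gait-velocity ceiling as 1.0 cm/s, but the pilot criterion that C.7 cites is 1 m/sec, which is 100 times higher

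*Combined protocol and SAP*

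**What the plan says.** The gait-velocity criterion is stated twice, in separately written lists. C.7, inclusion item 5, sets an upper limit of "1.0cm/s (same criterion was used in our pilot study"). E.1, general inclusion item 5, reads "Gait velocity ≤ 1.0 cm/s" and adds no explanation.

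The pilot is described in B.5.c. Its participants were frail seniors who exercised at most once a week and had "gait speed < 1 m/sec". That is the only place where the protocol gives the pilot's gait criterion.

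Three other parts of the plan bear on which scale is meant:

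- C.8 lists three balancing variables for randomization, one of which is "NPW speed $<$ or $>$ 70 cm/s".
- C.15.e returns to the 70 cm/s cut, explains why slow walkers are not excluded, and adds: "We will stratify analysis by this cutscore and examine effects".
- C.12.1.a measures gait on a "28-foot computerized mat (20-feet recording surface") and names speed in cm/s as the outcome.

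**The concern.** C.7 says that the trial and the pilot share one criterion, yet the two printed values differ by a factor of 100. Nothing in C.7 or E.1 flags or corrects the difference, and none of the amendment summaries supplied mentions this item. The same unit appears in both lists, so checking one against the other does not expose the slip.

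This threshold decides who may be randomized. Gait speed is recorded in cm/s, so a literal check compares cm/s with cm/s, and essentially every ambulatory participant would fail it. The DSMB interim reports described in E.8.e must contain "Assessments of whether study personnel have followed eligibility criteria and other protocol requirements". An adherence check of that kind needs a criterion that can be applied as printed.

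**Working it through.** **Inputs**

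| Quantity | Value | Section |
|---|---|---|
| Ceiling, first list | 1.0 cm/s, said to be the pilot criterion | C.7, item 5 |
| Ceiling, second list | 1.0 cm/s | E.1, item 5 |
| Pilot criterion | below 1 m/sec | B.5.c |
| Randomization and stratification cut | 70 cm/s | C.8, C.15.e |
| Recording surface | 20 feet | C.12.1.a |
| NPW difference used for power | 5 cm/s | C.14.1.b |

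**Step 1. Try to reproduce the printed ceiling from the criterion it cites.** 1 m/sec × 100 cm/m = 100 cm/s. The printed figure is 1.0 cm/s, and 100 / 1.0 = 100. The figure is not reproduced. The digits agree and the unit does not.

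**Step 2. Compare with the 70 cm/s cut.** Under a 1.0 cm/s ceiling the fastest eligible person walks at 1.0 cm/s, and 70 / 1.0 = 70, so the cut lies at 70 times the ceiling. The upper level of that balancing variable would be empty, and the stratified analysis in C.15.e would have a single stratum. Under a 100 cm/s ceiling, the eligible range of 70 to 100 cm/s fills the upper level and the design is coherent.

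**Step 3. Compare with the walkway.** 20 ft × 30.48 cm/ft = 609.6 cm. Crossing time = distance / speed:

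- at 1.0 cm/s: 609.6 / 1.0 = 609.6 s, or 609.6 / 60 = 10.2 min
- at 70 cm/s: 609.6 / 70 = 8.7 s
- at 100 cm/s: 609.6 / 100 = 6.1 s

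Read literally, an eligible person would need at least 10 minutes to cross the recording surface.

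**Step 4. Compare with the planned effect.** 5 / 1.0 = 5, so the NPW difference used for power would be five times the highest eligible baseline speed.

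**Step 5. See whether the ceiling enters any calculation.** The sample-size inputs in C.14.1.b are SDs of 12 cm/s, 20 cm/s and 1.5 points, and differences of 5 cm/s, 10 cm/s and 0.5 points. The interim rule in E.8.h uses an alpha of 0.003, conditional power below 10% and a difference of 4 cm/s. The ceiling appears in neither. The intention-to-treat definition in C.14.1.a keeps everyone who is randomized "regardless of adherence with entry criteria". The 169 evaluable and 210 enrolled per group therefore do not depend on the printed unit.

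**The case against.** The strongest reply is that this is an obvious slip which corrects itself. C.7 points to the pilot in the same line, B.5.c gives the pilot's unit, the 70 cm/s cut shows the scale, and nobody could apply 1.0 cm/s because almost nobody would qualify. E.1 opens by referring the reader to Section C for the criteria. There are also points at which the slip could be caught: study clinicians settle final eligibility (C.6), a manual of operations is planned (C.11), and the DSMB reviews the protocol with the team before data collection and may ask for clarification (E.8.c). On this view the crossing time and the empty level are only a demonstration of absurdity, and no participant is shown to have been wrongly enrolled or excluded.

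Most of this is fair. The intent is evident, and the figures in steps 2 to 4 show that the printed value cannot be meant; they do not measure harm. What does not follow is that the text may stand. The reference from E.1 leads to C.7, which carries the same misprint, so the reader must go on to B.5.c to recover the unit. The planned safeguards might catch the error, but the documents do not show that any of them did.

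It can also be said that the pilot used a strict inequality while both trial lists use ≤. That is true, but it matters only for someone exactly at the limit. The two trial lists agree with each other, and the pilot's sign describes a completed study.

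**Conclusion.** The point holds. The ceiling in C.7 item 5 and E.1 item 5 is misprinted by a factor of exactly 100 relative to the pilot criterion that C.7 names as its source. The 70 cm/s cut in C.8 and C.15.e independently shows that 1.0 cm/s cannot be the working value.

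The reach is narrow: the eligibility text, and any check or report made against it. The effect on sample size, power, the interim rule and the intention-to-treat analysis is nil. The conclusion needs no outside source. It rests on the protocol's own statement that the two criteria are the same, on the unit given in B.5.c, and on 1 m = 100 cm.

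**What to change.** - Have the investigators confirm the intended ceiling and reconcile B.5.c, C.7 and E.1. The pilot criterion that C.7 cites corresponds to 100 cm/s, or 1.0 m/s.
- Correct the unit in C.7 item 5 and in E.1 item 5 together, so that the two lists stay in agreement. The ≤ sign can remain, since both lists already use it.
- Use the confirmed value in the eligibility assessments reported to the DSMB under E.8.e.

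The cost is a unit correction in two lines. Design, sample size and analysis do not change.
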